NCT03309956

Protocol: AAAR5436

Principal Investigator: [name]

Title: Comparison of Holter with Leadless Patch Ambulatory Electrocardiographic Monitoring in Children

Version Date (Last IRB Approved): 9/26/2018

Study Purpose and Rationale:

The utility of ambulatory electrocardiography has been reported using a variety of devices, including the short-term (24- to 48-hour) Holter monitor and the longer term event monitor (7-30 days). Each monitoring modality has its strengths and limitations. The Holter monitor can detect asymptomatic arrhythmias by continuously recording, however the multiple leads are cumbersome and it is not ideal for capturing infrequent arrhythmias because of the short wear time. The Holter monitor's ability to detect an arrhythmia, or diagnostic yield, was 10% in a retrospective study of 1319 children. The event monitor is preferred for infrequent arrhythmias, however it requires cognitive capacity to press a trigger button, and patient compliance may be difficult in the pediatric population. The adhesive patch monitor (Zio Patch; iRhythm Technologies, San Francisco, California) is a single-lead, intermediate-duration, water-resistant adhesive patch monitoring device that can continuously record for up to 14 days. The Zio patch has demonstrated great utility in the adult population as it detected more arrhythmias in the first 24 hours as compared with the Holter monitor when worn simultaneously. In a retrospective study of 3,209 pediatric patients across the United States who used the Zio patch, the diagnostic yield was 12%. While both the Holter and the Zio patch are continuously recording and are able to detect asymptomatic arrhythmias, to date there has been no direct comparisons of the diagnostic yield (ability to detect an arrhythmia) of the Holter monitor versus the Zio patch in the pediatric population.

Study Design:

Pediatric patients less than or equal to 21 years at Children's Hospital of New York (CHONY) who are referred for ambulatory ECG monitoring will be consented and enrolled prospectively to have the Holter monitor and the Zio patch placed simultaneously in the pediatric cardiology clinic. Patients will be instructed to wear both devices for 48 hours. Demographic data will be collected, including date of birth, age, gender, weight, height, chest circumference, body surface area, indication for ambulatory ECG monitoring, prior congenital heart disease, prior cardiac surgery, and prior Holter or Zio patch use. A one page patient satisfaction survey will be given to the patient and parent/guardian after completion of the study to compare the comfort, interference with daily activities, adverse events (such as skin irritation or if either device fell off), and preference for each device. Holter monitors will be returned to the clinic along with the patient satisfaction survey, and the Zio patch will be mailed back to manufacturer headquarters and the report will be returned to us. Primary Objective: This prospective study aims to compare the diagnostic yield of the Holter monitor versus the Zio patch in children by having patients wear both devices simultaneously for 48 hours. We will compare the incidence of specific abnormal heart rhythms using each device, specifically supraventricular tachycardia 4 beats (SVT), ventricular tachycardia 4 beats (VT), advanced second degree or complete heart block, atrial flutter or fibrillation (AF), pause > 3 seconds, premature ventricular contractions (PVCs) > 5%, premature atrial contraction (PACs) > 5%, and presence of preexcitation suggestive of Wolff-Parkinson-White syndrome (WPW). Secondary objective: We will compare the minimum, maximum, and average heart rates, as well as the percent analyzable data for each device over the 48 hours. Tertiary objective: To determine if age, weight, gender, presence of congenital heart disease, or prior cardiac surgery had an effect on diagnostic yield of Holter monitor versus the Zio patch. Quaternary objective: To compare the patient and/or parental satisfaction for the Holter monitor versus the Zio patch using a one page survey at the end of the 48 hour study.

Statistical Procedures:

Descriptive statistics will be used for patient demographics and survey results. To compare presence or absence of any of the clinically significant arrhythmias (SVT > 4 beats, VT > 4 beats, advanced second degree or complete AV block, atrial fibrillation or flutter, pause > 2 seconds, PVCs > 5%) over 48 hours, McNemar's test will be used. Further subgroup analysis of each of the arrhythmia types can be done between the 2 devices using McNemar's test again. Logistic regression will be used to determine if age, weight, gender, presence of congenital heart disease, or prior cardiac surgery has an effect on diagnostic yield of Holter monitor versus the Zio patch. Using a power of 80% and allowing for 25% variability, the number of patients needed for the study was determined to be 255 using McNemar's test. We anticipate enrolling about 260 patients in this study.

Study Procedures:

Informed consent will be obtained in a private room in the pediatric cardiology clinic. If the patient agrees to participate in the research, the Holter monitor and the Zio patch will be placed on the patient in that private room. The Holter monitor will be returned to the clinic and the Zio patch will be returned in the mail, per protocol from the manufacturers. The results of both ambulatory ECG monitors will become part of the patient's confidential medical record.

After the data is collected, it will be de-identified and stored in a password protected electronic database on an encrypted endpoint (desktop and laptop computer). The patient satisfaction survey will be a hardcopy that will be stored in a binder locked inside the filing cabinet of the study coordinator. Only research investigators will have access to the electronic database or the binder of patient satisfaction surveys.

Study Devices:

Device name: Holter

Device description: Traditional ambulatory electrocardiographic monitor

Device Model/Version #: H3+ Digital Holter Recorder

Already approved by FDA and used as gold standard

Device name: Zio Patch

Device description: Leadless ambulatory patch electrocardiographic monitor

Device Model/Version #: Zio XT

FDA approved in adults, off-label use in children. This is a Nonsignificant Risk device (21 CFR 812.2(b)); no more than Minimal Risk (45 CFR 46.404/21 CFR 50.51; i.e., 'Section 404').

Research Question(s)/Hypothesis(es):

Primary objective: This prospective study aims to compare the diagnostic yield (ability to detect an arrhythmia) of the Holter monitor versus the Zio patch in children by having patients wear both devices simultaneously for 48 hours. We will compare the incidence of specific abnormal heart rhythms in children using each device, specifically supraventricular tachycardia 4 beats (SVT), ventricular tachycardia 4 beats (VT), advanced second degree or complete heart block, atrial flutter or fibrillation (AF), pause > 3 seconds, premature ventricular contractions (PVCs) > 5%, premature atrial contractions (PACs) > 5%, and presence of preexcitation suggestive of Wolf Parkinson White syndrome (WPW).

Secondary objective: We will compare the minimum, maximum, and average heart rates, as well as the percent analyzable data for each device over the 48 hours. Tertiary objective: To determine if age, weight, gender, presence of congenital heart disease, or prior cardiac surgery had an effect on diagnostic yield of Holter monitor versus the Zio patch. Quaternary objective: To compare the patient and/or parental satisfaction for the Holter monitor versus the Zio patch using a one page survey at the end of the 48 hour study. Hypotheses: 1. There will be no difference in the diagnostic yield or the heart rate parameters (maximum, minimum, or average heart rate, percent analyzable data) of the Zio patch compared to the Holter monitor during the 48 hours of monitoring. 2. Age, weight, gender, presence of congenital heart disease, or prior cardiac surgery will not affect diagnostic yield of the Holter versus the Zio patch. 3. Patients will prefer the Zio patch over the Holter monitor based on the patient satisfaction survey.

Scientific Abstract:

Ambulatory electrocardiographic (ECG) monitoring is common diagnostic tool used to detect arrhythmias in the outpatient setting. The traditional Holter monitor is the gold standard ambulatory ECG monitoring device that is commonly used in children. However, it has multiple leads and can be cumbersome. The Zio patch is a new single-lead patch ECG monitor that has been FDA approved for use in adults and has been used off-label in children for several years. While both the Holter and the Zio patch are continuously recording and are able to detect asymptomatic arrhythmias, to date there has been no direct comparisons of the diagnostic yield (ability to detect an arrhythmia) of the Holter monitor versus the Zio patch in the pediatric population. This prospective study aims to compare the diagnostic yield, heart rate parameters, and patient satisfaction of the Holter versus the Zio patch in pediatrics. Patients less than or equal to 21 years of age referred for ambulatory ECG monitoring at the pediatric cardiology clinic at Children's Hospital of New York (CHONY) will be recruited to participate in the study. ECG technicians will obtain informed consent and place the Holter monitor and Zio patch simultaneously on the patient. After 48 hours of monitoring, the patient will mail the Zio patch to the manufacturer and the return the Holter monitor to the clinic. The patient satisfaction survey will be submitted to the researchers in clinic upon completion of the study. Descriptive statistics will be used for patient demographics and survey results. To compare presence or absence of any of the clinically significant arrhythmias (supraventricular tachycardia (SVT) > 4 beats, ventricular tachycardia (VT) > 4 beats, advanced second degree or complete atrioventricular block, atrial fibrillation or flutter, pause > 2 seconds, premature ventricular contractions (PVCs) > 5%) over 48 hours, McNemar's test will be used. Further subgroup analysis of each of the arrhythmia types will be done using McNemar's test again. Logistic regression will be used to determine if age, weight, gender, presence of congenital heart disease, or prior cardiac surgery has an effect on diagnostic yield of Holter monitor versus the Zio patch.

Lay Abstract:

Ambulatory electrocardiographic (ECG) monitoring is common diagnostic tool used to detect arrhythmias in the outpatient setting. The traditional Holter monitor is the gold standard ambulatory ECG monitoring device that is commonly used in children. However, it has multiple leads and can be cumbersome. The Zio patch is a new single lead patch ECG monitor that has been FDA approved for use in adults and has been used off-label in children for several years. While both the Holter and the Zio patch are continuously recording and are able to detect asymptomatic arrhythmias, to date there has been no direct comparisons of the diagnostic yield (ability to detect an arrhythmia) of the Holter

monitor versus the Zio patch in the pediatric population. This prospective study aims to compare the diagnostic yield, heart rate parameters, and patient satisfaction of the Holter versus the Zio patch in pediatrics. Patients less than or equal to 21 years of age referred for ambulatory ECG monitoring at the pediatric cardiology clinic at Children's Hospital of New York (CHONY) will simultaneously wear both the Holter and the Zio for 48 hours. Data parameters will be compared using descriptive statistics, McNemar's test, and logistic regression.

Subject Population Justification:

Any patient from birth through 21 years of age who is referred for ambulatory ECG monitoring at CHONY will be recruited for participation in this study. In a large retrospective study using the Zio patch, neonates (under 1 month of age) have used the Zio patch off label, therefore this study will prospectively study the device in all ages from birth through 21 years. We will obtain informed consent in English or in Spanish. Target enrollment is 260 participants.

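### Hypothesis 3 is about patients' preference, but the survey plan does not separate patient from parent answers and gives no interval or test

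*Combined protocol and SAP*

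**What the plan says.** - **Research Question(s)/Hypothesis(es), Hypothesis 3:** "Patients will prefer the Zio patch over the Holter monitor based on the patient satisfaction survey". It is directional, and its subject is patients.
- **Same section, quaternary objective:** "To compare the patient and/or parental satisfaction for the Holter monitor versus the Zio patch using a one page survey". This is wider than the hypothesis, because parental satisfaction alone would meet it.
- **Study Design:** "A one page patient satisfaction survey will be given to the patient and parent/guardian after completion of the study". The listed content is comfort, interference with daily activities, adverse events and device preference.
- **Subject Population Justification:** "Any patient from birth through 21 years of age who is referred for ambulatory ECG monitoring at CHONY will be recruited". The section mentions neonates expressly.
- **Statistical Procedures, repeated in the Scientific Abstract:** "Descriptive statistics will be used for patient demographics and survey results". McNemar's test and logistic regression are assigned to arrhythmia detection and diagnostic yield, not to the survey.

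The documents do not say who answers at which age, whether the two views are recorded or reported separately, how disagreement, no preference or an unreturned form is handled, or what result would count for or against Hypothesis 3. The form itself is not in the documents.

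**The concern.** Two things do not line up with the hypothesis.

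The first is the analysis. A directional prediction is paired with a method that, as stated, includes neither an interval nor a test. Any share above one half could then be presented as agreement with the prediction, however close to an even split.

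The second is the respondent. The prediction concerns patients, but an infant cannot state a preference, so that child's form can only carry an adult's view. An older child's form may carry the child's view, the parent's, or both. If these are summarised in one percentage, the result depends on the age mix of the children who happen to enrol, and it cannot be attributed to patients.

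At stake is whether a statement that patients prefer the patch can be supported from the survey. No result on diagnostic yield or heart rate depends on it.

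**Working it through.** **The plan's own figure.** None is given for the survey. The only calculated figure is for McNemar's test on yield: "Using a power of 80% and allowing for 25% variability, the number of patients needed for the study was determined to be 255". Its alpha and expected difference are not stated and the 25% is not defined, so it cannot be reproduced. Nothing below depends on it. The one number used from the documents is planned enrolment: "We anticipate enrolling about 260 patients in this study".

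**Assumptions.** One stated preference per child, independent answers, no ties, two-sided alpha 0.05. The documents give no age distribution, so the number able to self-report is shown as a range.

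**1. Chance.** Under an even split the number preferring Zio is X ~ Binomial(n, 0.5), and the exact two-sided p-value is 2 × P(X ≥ x).

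- x = 143, n = 260: 143/260 = 55.0%, p = 0.121, Wilson 95% CI 48.9% to 60.9%.
- With n = 260 and a true even split, P(X ≥ 131) = 0.475. A bare majority for Zio would appear nearly half the time.

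The smallest count giving p < 0.05, by number of answers:

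| Answers n | Count needed | Share |
|---|---|---|
| 260 | 147 | 56.5% |
| 200 | 115 | 57.5% |
| 150 | 88 | 58.7% |
| 130 | 77 | 59.2% |
| 100 | 61 | 61.0% |
| 65 | 41 | 63.1% |

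**2. Is the sample large enough?** The 95% half-width at 50% is 1.96 × √(0.25/n).

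- n = 260: 6.1 points. The sign test has 33% power if 55% truly prefer Zio, 88.5% at 60% and 99.8% at 65%.
- n = 130: 8.6 points, and 61% power at 60%.
- n = 65: 12.2 points, and 36% power at 60%.

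If most children could answer for themselves, sample size would not be the obstacle.

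**3. Respondent.** Let s be the share of answers that are parental. Pooled preference = (1 − s) × patient rate + s × parent rate. As an illustration only, assume that patients split 50/50 and parents favour Zio at 70%. The probability that a sign test on 260 pooled answers rejects 50% is then:

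| Parental share s | Pooled preference | P(reject) |
|---|---|---|
| 25% | 0.75 × 50 + 0.25 × 70 = 55% | 33% |
| 50% | 0.50 × 50 + 0.50 × 70 = 60% | 88.5% |
| 75% | 0.25 × 50 + 0.75 × 70 = 65% | 99.8% |

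In every row patients have no preference. Adding a test to pooled answers would therefore not repair the plan, and a larger sample would make the misattribution look firmer. The 70% and the shares are assumptions; the documents give neither.

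**The case against.** Describing a satisfaction survey without a formal test is a legitimate choice for the lowest-ranked objective. Descriptive statistics do not exclude a confidence interval, and no decision rule is stated that would treat any majority as proof. The objective openly includes parents, so their answers are an intended part of the measure. Age is collected, which would allow a breakdown, and the form may already identify who answered.

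Much of this stands, and it limits the point in two ways.

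- A reader might infer that patient and parent answers will be pooled. The documents do not say so; they only leave it open.
- A reader might infer that the survey cannot support any conclusion, or that Hypothesis 3 can be neither confirmed nor refuted. That is too strong. About 260 answers give roughly ±6 points, so a clear majority either way would be informative, and a proportion with an interval among self-reporters would be enough.

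The documents also give no ground for saying why parents might favour one device.

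What the objection does not answer is that Hypothesis 3 is one of three numbered hypotheses and names patients. No text ties the answers to patients or says how the estimate's uncertainty will be shown. An age breakdown helps only partly, because it does not reveal who filled in an older child's form.

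**Conclusion.** The point holds as a mismatch between Hypothesis 3 and its planned analysis. Followed as written, the plan does not specify the respondent, the interval or test, or the criterion needed to conclude that patients prefer the Zio patch.

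On chance alone, a share below about 56.5% of 260 answers, or below 61% of 100, would not be distinguishable from an even split at two-sided 5%. This assumes one stated preference per child and no ties. The respondent question is the more serious half, because a larger sample does not remove it. Its size cannot be computed from the documents, and the 60% pooled figure above is an illustration.

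The change is worth making because it is cheap. It concerns the quaternary objective only and leaves the primary comparison untouched.

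**What to change.** 1. Name the device-preference item as the outcome for Hypothesis 3.
2. Record on the form who answered, with one preference line for the patient and another for the parent/guardian. A single tick-box would not capture two views on one page.
3. Report the two groups separately. For each, give the proportion preferring Zio among those stating a preference, with a 95% CI and an exact sign test against 50%. Add the numbers with no preference and with no returned survey.
4. Base any statement about patients on self-report only, and say in the plan who counts as self-reporting. Alternatively, reword Hypothesis 3 to patients and/or parents, so that it matches the objective.
5. Leave the other survey items descriptive.

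**Cost.** A small change to the survey form, with whatever approval that needs, and a few sentences in Statistical Procedures. No patients, visits or procedures are added. The interval for the self-report group will be wider than for all 260 (for example ±8.6 points at 130 answers against ±6.1 at 260), and the documents do not give that group's size. The form should be changed before surveys are collected, because a respondent not recorded at the time may not be recoverable once the data are de-identified.

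### The primary McNemar composite uses a different rhythm list and pause threshold from the primary objective

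*Combined protocol and SAP*

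**What the plan says.** The combined protocol and SAP defines the rhythms of interest in four places, and they fall into two pairs.

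- **Objective.** The primary objective in Study Design names eight findings, the last four being "pause > 3 seconds, premature ventricular contractions (PVCs) > 5%, premature atrial contraction (PACs) > 5%, and presence of preexcitation" suggestive of WPW. Research Question(s)/Hypothesis(es) repeats the list with the same threshold: "pause > 3 seconds, premature ventricular contractions (PVCs) > 5%, premature atrial contractions (PACs) > 5%, and presence of preexcitation".
- **Test.** Statistical Procedures applies McNemar's test to the presence or absence of any of six findings, the last three being "atrial fibrillation or flutter, pause > 2 seconds, PVCs > 5%) over 48 hours". The Scientific Abstract repeats this: "pause > 2 seconds, premature ventricular contractions (PVCs) > 5%) over 48 hours".

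Tests by rhythm type are also mentioned. Statistical Procedures words them as optional ("Further subgroup analysis of each of the arrhythmia types can be done between the 2 devices") and the Scientific Abstract as definite ("Further subgroup analysis of each of the arrhythmia types will be done").

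Hypothesis 1 begins "There will be no difference in the diagnostic yield". The logistic regression asks whether age, weight, gender, congenital heart disease or "prior cardiac surgery has an effect on diagnostic yield of Holter monitor versus the Zio patch". Neither statement says which list defines the yield.

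**The concern.** Diagnostic yield is the primary quantity of this study, and the plan defines it in two ways. A child whose only finding is a pause longer than 2 and up to 3 seconds is positive in the McNemar composite and negative under the objective. A child with only PACs above 5%, or only preexcitation, is negative in the composite and positive under the objective. Neither definition contains the other, so the test does not answer exactly the question that the objective and hypothesis 1 ask.

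No section says which list takes precedence when they disagree. Two analysts could follow the document faithfully and code the same child differently, and the choice could be made after the results are seen.

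**Working it through.** This is first a comparison of texts. The plan gives no figure on this point to reproduce. The sample-size statement names no rhythm list, so it does not help to decide between the two.

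**Step 1: the lists side by side.**

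| Finding | Objective (Study Design; Research Questions) | McNemar composite (Statistical Procedures; Scientific Abstract) |
|---|---|---|
| SVT | yes | yes |
| VT | yes | yes |
| Advanced/complete AV block | yes | yes |
| Atrial fibrillation/flutter | yes | yes |
| PVCs > 5% | yes | yes |
| Pause | > 3 s | > 2 s |
| PACs > 5% | yes | no |
| Preexcitation | yes | no |

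The count is 8 = 5 matching in kind + 1 with a different threshold + 2 absent from the test. The test list adds nothing that the objective lacks. The objective gives SVT and VT as 4 beats without a comparison sign, where the test list has > 4. I do not count this, because a symbol may have been lost in text extraction.

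**Step 2: slip or subset?** Each version appears twice with a legible numeral, so this is not one typing error. Statistical Procedures labels its six as clinically significant, which might signal a chosen subset of the eight. A subset would keep the pause criterion or tighten it. Going from > 3 s to > 2 s loosens it.

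**Step 3: do the tests by type close the gap?** Not clearly. The sentence follows the six-item list and is optional in one section and definite in the other. Even if it covers PACs and preexcitation, both stay outside the any-arrhythmia comparison and the pause conflict remains.

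**Step 4: effect on the result.** McNemar's test uses only patients on whom the devices disagree. A child whose only finding is a reclassified rhythm, scored alike by both devices, adds 0 discordant pairs and leaves p unchanged. The documents give no rates for PACs, preexcitation or pauses of 2 to 3 s, so the effect cannot be computed.

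An illustration needs assumptions: discordance of 5% to 10%, a two-sided 0.05 criterion (the plan states no alpha), and splits chosen to be borderline. With the plan's 255 patients:

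- 255 × 0.05 = 12.75, about 13 discordant pairs
- 255 × 0.10 = 25.5, about 26 discordant pairs

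The exact two-sided McNemar p for cells b < c is 2 × Σ(k = 0 to b) C(b + c, k) / 2^(b + c).

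| Split | p | One pair added to the smaller cell | p | One pair added to the larger cell | p |
|---|---|---|---|---|---|
| 2 v 11 | 0.0225 | 3 v 11 | 0.0574 | 2 v 12 | 0.013 |
| 7 v 19 | 0.0290 | 8 v 19 | 0.0522 | 7 v 20 | 0.019 |

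For example, 2 v 11 gives 2 × (1 + 13 + 78) / 8192 = 0.0225.

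**The case against.** The strongest defence is that the two lists serve different purposes. The objective first speaks of overall yield and then of the incidence of specific rhythms. The analysis text likewise has two tiers: any clinically significant arrhythmia, then each type. On that reading the six are the composite, the eight are for comparisons by type, and leaving PACs and preexcitation out of the composite is not an error. Only the six-item list is tied to a test, in both places where the test is described, so a tested outcome was named in advance. The regression sentence follows soon after that outcome and most naturally uses it.

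Part of this stands. The six-item list is the only one attached to a test, and the two omissions may be intended. But no section says so, and the reading cannot account for a composite with a looser pause criterion than the objective it serves. The pause conflict therefore survives every reading.

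A second objection is that no harm is shown. Either list would be applied to both devices in the same children, so no bias between devices is demonstrated. The illustrative splits are the only ones that cross 0.05 when one pair is added: 2 v 11 among the 7 possible splits of 13 pairs, and 7 v 19 among the 14 possible splits of 26. This is fair, and it limits what the illustration can show. It does not remove the contradiction in the primary endpoint.

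**Conclusion.** The concern holds. The pause threshold of the primary endpoint is contradictory: > 3 s in the objective and > 2 s in the test, each stated twice. The omission of PACs above 5% and preexcitation from the composite is unexplained; it may be deliberate, but the plan does not say so. The logistic regression takes on the same ambiguity because it uses diagnostic yield without naming a list.

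The effect on the McNemar result can be neither sized nor signed from the documents. At borderline splits a single pair could move p across an assumed 0.05; elsewhere one pair would not change the conclusion. The verdict rests on the text and not on those figures. It must be fixed, because the primary endpoint is contradictory as written and a reader cannot resolve it.

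**What to change.** Before data lock, reconcile Study Design, Statistical Procedures, Research Question(s)/Hypothesis(es) and the Scientific Abstract to one prespecified rhythm list with one pause threshold. Score it identically on both devices and use it in the primary objective, the McNemar composite and the logistic regression.

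- Either put every rhythm that the objective names into the composite, or restate the objective to match the composite.
- The sponsor should state which pause threshold was intended. This review takes no position on which is right.
- State whether the McNemar tests by type are planned or optional, and whether they cover PACs above 5% and preexcitation.
- Report the other list as a named sensitivity analysis.

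The cost is wording changes in the objective and analysis sections and one extra table. This assumes that both device reports allow every listed rhythm to be scored; the documents do not describe the contents of either report.

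### The per-rhythm comparison, part of the primary objective, rests on McNemar p-values alone; for rare rhythms these say little, so paired counts with exact intervals should be reported

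*Combined protocol and SAP*

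**What the plan says.** The Primary Objective paragraph under Study Design goes beyond overall yield: "We will compare the incidence of specific abnormal heart rhythms using each device". It then lists eight rhythms, and Research Question(s)/Hypothesis(es) repeats the list.

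Statistical Procedures tests the presence of any clinically significant arrhythmia by McNemar's test, using a list of six rhythms. It then adds: "Further subgroup analysis of each of the arrhythmia types can be done between the 2 devices using McNemar's test again". The Scientific Abstract turns the option into a commitment: "Further subgroup analysis of each of the arrhythmia types will be done using McNemar's test again". No other method for the individual rhythms appears.

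On size, Statistical Procedures says "We anticipate enrolling about 260 patients in this study". Study Purpose and Rationale says that the Holter yield "was 10% in a retrospective study of 1319 children" and gives 12% for the Zio patch from a separate retrospective series of 3,209 patients.

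The documents do not give a rate for any single rhythm, the version of McNemar's test, the significance level, per-rhythm power, an agreement measure, a confidence interval, or a rule for reading a non-significant per-rhythm result. The first hypothesis is that yield will not differ between the devices, and it has no margin.

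**The concern.** McNemar's test uses only discordant children, those in whom one device found the rhythm and the other did not. When few children have a rhythm, the discordant pairs are fewer still, and the p-value may be unable to reach 0.05 however the patch performs. A large p-value then reflects the small count and says little about agreement.

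Two features of the plan make this matter. Individual rhythms are named in the primary objective, so readers will look for a result on each. The stated hypothesis is one of no difference, without a margin, so a non-significant p-value could be taken as support for it. For an uncommon rhythm, a patch that missed most or all cases could then appear to match the Holter.

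The unnamed version adds a further problem, because the same small table can fall on either side of 0.05 depending on which version is run.

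**Working it through.** **The plan's own figure.** The stated sample size is 255, with 80% power and an allowance of 25% for variability. It cannot be reproduced: the significance level, sidedness and target difference are not given, and the 25% is not defined. If the 25% were the discordant share p_d, the usual formula n = (1.96√p_d + 0.8416√(p_d − d²))²/d² returns 255 at a difference d of about 0.087, two-sided 0.05. The calculation names no individual rhythm, so it does not bear on this point.

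**Inputs.** Enrolment is 260 (Statistical Procedures). Overall yields are 10% and 12% (Study Purpose and Rationale). The number of rhythms is 6 (Statistical Procedures) or 8 (Primary Objective). Two-sided 0.05 is my assumption.

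**Step 1: expected positives.** 260 × 0.10 = 26 and 260 × 0.12 = 31.2. On an even split, 26/8 = 3.3 and 31.2/8 = 3.9; 26/6 = 4.3 and 31.2/6 = 5.2. The average is therefore 3.3 to 5.2 children per rhythm.

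**Step 2: p-value in the extreme case.** Suppose all n positives are found by the Holter and none by the patch. The exact p is 2 × 0.5ⁿ. The continuity-corrected χ² is (n − 1)²/n and the uncorrected χ² is n, each on 1 degree of freedom.

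| n v 0 | Exact | Corrected | Uncorrected |
|---|---|---|---|
| 3 | 0.25 | 0.248 | 0.083 |
| 4 | 0.125 | 0.134 | 0.0455 |
| 5 | 0.0625 | 0.074 | 0.025 |
| 6 | 0.031 | 0.041 | 0.014 |

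The smallest one-way count giving p<0.05 is six for the exact and corrected tests and four for the uncorrected test. Mid-p (half the exact value here) needs five.

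**Step 3: chance of p<0.05 when the patch misses every case.** Take an assumed prevalence π and no Zio-only detections. The chance is P(Binomial(260, π) ≥ 6) for the exact test and P(Binomial(260, π) ≥ 4) for the uncorrected test.

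| Assumed π | Expected cases | Exact | Uncorrected |
|---|---|---|---|
| 1% | 2.6 | 4.8% | 26% |
| 2% | 5.2 | 42% | 76% |
| 3% | 7.8 | 79% | 95% |

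**Step 4: patch misses half the cases.** Replace π by π/2 in the same formulas. The chances are 0.2% (exact) and 4.3% (uncorrected) at 1% prevalence, 4.8% and 26% at 2%, and 19.8% and 55% at 3%.

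**Step 5: what an interval would show.** If the patch found 3 of 3 Holter-detected cases, the exact 95% lower limit is 0.025^(1/3) = 0.29, so the interval is 29% to 100%. The reader then sees how little three cases establish.

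**The case against.** **Version of the test.** A reader might infer that three to five positives can never give p<0.05. That holds for the exact and corrected tests only. The plan names no version, and the uncorrected test is significant at 4 v 0 and 5 v 0. At 2% prevalence it would detect a patch that missed every case 76% of the time. So the documents do not support saying that these tests return non-significance almost regardless of performance. The statement is confined to rhythms at about 1% or below, and to partial misses at the lower prevalences.

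**False positives.** A reader might also infer that the uncorrected test is generally too liberal. Its error is 12.5% given exactly four discordant pairs and 6.25% given five, but 0% at three, 3.1% at six and 1.6% at seven. Averaged over a Poisson number of discordant pairs with mean 1 to 5, it is 0.2% to 4.6%. The charge of excess false positives fails as a description of the procedure.

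**The counts.** The even split, one rhythm per child and the 1% to 3% prevalences are not in the documents, which also do not define what the 10% and 12% yields counted. Common rhythms could well exceed six cases. This stands, and it is why the result is given as a range. Unevenness does, however, leave some rhythms below the average, where every version does worse. The documents do not say which rhythms those would be.

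**The misreading.** Nothing says that a non-significant per-rhythm test will be read as agreement. The plan tests yield as a composite and calls the rhythm tests subgroup analysis, where low power is ordinary. This also stands: the misreading is a risk and not a stated intention. But the Primary Objective itself names the rhythms, and nothing in the plan guards against that reading.

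**Selection of rhythms.** Optional wording in one place and firm wording in another might suggest rhythms picked after the data are seen. Every rhythm is named in advance, so the documents show only an inconsistency to be settled.

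**Conclusion.** The point holds in a limited form. Part of the primary objective has only a McNemar p-value as its analysis, with no version named and no paired counts or intervals. For a rhythm present in about 1% of 260 children, even a patch that missed every case would reach p<0.05 only 4.8% (exact) to 26% (uncorrected) of the time; if it missed half, 0.2% to 4.3%. For such rhythms the p-value is uninformative under any version. At 2% to 3% the answer depends on the version and on whether the misses are total or partial.

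The yields and enrolment come from the documents. The prevalences, the even split, the two-sided 0.05 level and the absence of Zio-only cases are assumptions. The threshold counts of six and four follow from the test itself, given the 0.05 level. The composite comparison is not affected. This should be changed, and the remedy uses data the study already collects.

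**What to change.** In Statistical Procedures and in the Scientific Abstract, replace the sentence on per-rhythm tests with wording to this effect:

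> For every listed rhythm we will report the numbers of children in whom it was detected by both devices, by the Holter only and by the Zio only. We will give the proportion of each device's detections also found by the other, with exact 95% confidence intervals. Single-device detections of rare rhythms will be listed individually. Any per-rhythm p-value will be from the exact or mid-p McNemar test, and a non-significant value will not be taken as evidence of no difference.

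Use the firm form in both places, so that the analysis is committed for all rhythms, and reconcile the six-item and eight-item lists so that it is clear which rhythms the table covers. Dropping per-rhythm tests altogether is possible but is a matter of preference; keeping them beside the counts and intervals serves equally well.

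The cost is a change of wording and one extra table, with no new patients or data. The downside is that the report could not claim rhythm-by-rhythm equality for rare rhythms.
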